The primary outcome of this embedded trial will be the recruitment rate, i.e. the proportion of participants in each group who are randomised into the host trial. Secondary outcomes will include the proportion of patients in each group who are screened but do not go on to be randomised, and the cost effectiveness of the intervention.

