10.6.1 Recruitment SWAT

An 'intention-to-treat' analysis will be performed including all randomised sites analysed in the SWAT group to which they were allocated.

Both demographic characteristics, including age, sex, and ethnic group of randomised participants and site characteristics, including geographical location and catchment size, will be presented descriptively as mean (standard deviation) or number (%), as appropriate.

The primary analysis will compare the difference in recruitment rates between those receiving the animation in addition to the PIL and those not receiving the animation. This outcome will be analysed using mixed effect logistic regression with a fixed effect for SWAT allocation and a random intercept for site.

Secondary analysis: The difference in the proportion of those responding to a recruitment invitation who received the animation in addition to the PIL but who do not go on to be randomised, and those not receiving the animation but who do not go on to be randomised will also be analysed using a similar model to the primary outcome.

The difference in cost per recruited participant between those offered the animation and those not offered the animation will be calculated. In addition to the direct costs of the animation, it may also be necessary to include the cost of staff time spent administering the recruitment packs.

The following sensitivity analyses will be performed for the primary analysis:

• Excluding participants who did/could not receive allocation as randomised.

Subgroup analysis may also be performed for key demographic subgroups (e.g. age, gender, ethnicity) by adding interaction terms to the logistic regression or Cox regression model, where the sample size is deemed sufficiently large.

Where available, a meta-analysis, including data from existing SWATs will be undertaken to incorporate the results from this SWAT.

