10.6.2 Retention SWAT

An 'intention-to-treat' analysis will be performed including all randomised participants analysed in the SWAT group to which they were allocated.

Demographic characteristics, including age, sex, and ethnic group, will be presented descriptively as mean (standard deviation) or number (%), as appropriate.

Primary analysis: Comparison of the questionnaire response rate between the SWAT groups will use logistic regression. The regression model will include the randomised group factor and the SWAT stratification factor (i.e., host trial intervention arms). The between-groups difference will be presented as number (%) and as both adjusted absolute (i.e., risk difference) and relative (i.e., odds ratio or relative risk) effect estimates, with 95% confidence intervals from the logistic regression model.

Any randomised participant who does not provide outcome data for any reason (including participants who were deceased or withdrawn from the host trial) will be categorised as 'No' for the primary outcome.

Secondary analysis: The between-groups difference in time taken to collection of outcome data will be analysed using techniques suitable for time to response (event) data such as Kaplan-Meier curves, log-rank test or Cox regression (adjusted for SWAT stratification/minimisation factors). Time zero will be set as 'day before expected completion date' (equivalent to adding 1 to the time variable to avoid exclusion from the analysis set). The analysis of questionnaire

completeness will be as for the primary outcome. The incremental cost per participant retained will be calculated for the comparisons under evaluation as the difference in costs between the SWAT groups, divided by the difference between groups in completion rates. Direct costs of the retention strategies, and indirect costs associated with administering the strategies and the comparators will be included.

The following sensitivity analyses will be performed for the primary analysis:

- Excluding participants who did/could not receive allocation as randomised.
- Excluding participants who were retrospectively found to have died or withdrawn from the host trial before the expected completion date.

Subgroup analysis may also be performed for key demographic subgroups (e.g. age, gender, ethnicity) by adding interaction terms to the logistic regression or Cox regression model, where the sample size is deemed sufficiently large.

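### The recruitment SWAT lists the animation's cost effectiveness as a secondary outcome, but its one stated calculation does not give the cost of an additional recruit and depends on a staff-time choice left open

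*Protocol*

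**What the plan says.** Section 4.5.1 of the protocol sets the effect measure of the recruitment SWAT: "The primary outcome of this embedded trial will be the recruitment rate", that is, the proportion randomised into the host trial. Its secondary outcomes include "the cost effectiveness of the intervention".

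Section 10.6.1 gives one economic calculation for this SWAT: "The difference in cost per recruited participant between those offered the animation and those not offered the animation will be calculated". On costs, it counts the direct cost of the animation and adds that "it may also be necessary to include the cost of staff time spent administering the recruitment packs".

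Section 10.6.2 treats the matching outcome of the retention SWAT differently: "The incremental cost per participant retained will be calculated for the comparisons under evaluation". The numerator of that ratio is the gap in cost between the two groups, and its denominator is the gap in their completion rates. The section also commits to counting both the direct costs of the strategies and the indirect costs of administering strategies and comparators.

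**The concern.** Cost effectiveness relates extra cost to extra effect. Here the effect is recruitment, so the natural question is what one more recruited participant costs. The stated calculation subtracts one group's average cost per recruit from the other's, which answers a different question.

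The result also depends on which costs are counted, and section 10.6.1 does not settle that. If only the animation's direct cost is counted, the comparison group costs nothing and the figure is simply the animation cost spread over the animation group's recruits. It is then positive even if the animation has no effect on recruitment. If costs common to both groups are added, the same data can give zero or a negative figure. A choice about staff time made after the data are in could therefore move the reported finding from extra cost to saving.

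What is at stake is one secondary outcome of an embedded study, and how far its result can be used by others deciding whether to fund an animation.

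**Working it through.** The protocol gives no cost, recruitment rate or result for this outcome, so there is no stated figure to reproduce. The numbers below are assumptions chosen to show how the measures behave.

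**Notation.** C0 and C1 are the total costs without and with the animation; R0 and R1 are the numbers recruited.

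- Planned figure (10.6.1): D = C1/R1 - C0/R0
- Incremental ratio (the form in 10.6.2): I = (C1 - C0)/(R1 - R0), for equal numbers approached

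The two are linked by D = [(R1 - R0)/R1] x (I - C0/R0). When the animation recruits more, D is negative exactly when an extra recruit costs less than the existing average cost per recruit.

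**Assumed inputs.** 500 patients approached per group; 30% recruited without the animation, so R0 = 150; 35% with it, so R1 = 175; animation £5,000 in total, or £10 per patient approached. The cost common to both groups is varied.

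| Common cost per patient approached | C0/R0 | C1/R1 | D | I |
|---|---|---|---|---|
| £0 | 0/150 = £0 | 5,000/175 = £28.57 | +£28.57 | 5,000/25 = +£200 |
| £60 | 30,000/150 = £200 | 35,000/175 = £200 | £0 | 5,000/25 = +£200 |
| £100 | 50,000/150 = £333.33 | 55,000/175 = £314.29 | -£19.05 | 5,000/25 = +£200 |

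Check by the identity at £100: (25/175) x (200 - 333.33) = -19.05. The incremental ratio does not move because an equal per-patient cost cancels in C1 - C0.

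**Direct cost only.** With C0 = 0, D = 5,000/R1. For animation-group recruitment of 25%, 30%, 35% and 40%, R1 is 125, 150, 175 and 200, and D is +£40, +£33.33, +£28.57 and +£25. It is positive whether the animation harms recruitment, does nothing or helps.

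**Other assumed settings** (500 per group, 30% without the animation):

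- £50 common cost, £2,000 animation, 35%: D = 27,000/175 - 25,000/150 = -£12.38; I = 2,000/25 = +£80.
- £20, £2,000, 40%: D = 12,000/200 - 10,000/150 = -£6.67; I = 2,000/50 = +£40.
- £100, £10,000, 35%: D = 60,000/175 - 50,000/150 = +£9.52; I = 10,000/25 = +£400.

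The two measures can differ in sign or, with the same sign, widely in size. A sign difference with better recruitment needs common costs to be counted; with direct cost only and better recruitment the signs agree.

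**The case against.** The strongest defence is that the planned figure answers a real question. The host trial recruits to a fixed target, stated as 386 in section 10.1. For a fixed target, total recruitment cost is the target times the average cost per recruit, so the difference in averages shows which method fills the trial more cheaply. Take the £100 row, with costs scaling per patient approached. Reaching 386 costs 386/0.30 x £100 = £128,667 without the animation and 386/0.35 x £110 = £121,314 with it. The difference of about £7,350 is 386 x £19.05. A reader might infer that a negative figure is only an apparent saving, or that the planned measure is simply wrong. The documents do not support that: with full costs and a fixed target, the saving is real. This part of the defence stands. It needs costs common to both groups to be counted, however, and section 10.6.1 does not commit to that.

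Three further points deserve weight.

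- The incremental ratio is unstable or undefined when the rate difference is near zero. That is plausible in a site-randomised SWAT with no power calculation. The ratio can also turn negative when the animation recruits fewer: with direct cost only and 25% recruited, it is 5,000/(125 - 150) = -£200, which could be misread as a saving. This stands, and is why the components must be shown as well.
- A reader might see a contradiction between sections 10.6.1 and 10.6.2. They are separate studies with different outcomes, and nothing in the protocol plans to compare their economic results. The difference shows that a suitable form is already in use here, not that the text conflicts.
- Sections 4.5 and 10.6 point to separate repository protocols, which are not at hand and may say more. Section 10.6.1 nevertheless states a specific calculation and does not defer to them for another.

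**Conclusion.** The point holds in a limited form. The stated calculation is a legitimate budgeting summary when all recruitment costs are counted in both groups, but it does not give the cost of an additional recruit. With only the animation's direct cost counted, it cannot show cost effectiveness, because it is positive whatever happens to recruitment. With the cost items left open, its sign is open too: +£28.57 to -£19.05 in the illustration, against a constant +£200 per extra recruit.

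These amounts rest on assumed costs and rates, on equal numbers approached and on a common cost that is the same per patient in both groups. If the animation changes staff time per patient, the incremental ratio changes as well, and should. A reversal of sign is possible, not certain.

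The importance is low. It concerns one secondary outcome of an embedded study and leaves the host trial's analysis untouched.

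**What to change.** In section 10.6.1:

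- Define the cost-effectiveness measure as the incremental cost per additional participant recruited: the difference between SWAT groups in mean cost per patient approached, divided by the difference in recruitment rates. Costing per patient approached also allows for unequal group sizes, since sites rather than patients are allocated 1:1.
- Report the cost difference and the rate difference separately alongside the ratio, in particular when the rate difference is near zero.
- Keep the difference in average cost per recruit as a descriptive figure.
- State that the same cost items, including staff time, are counted in both groups.

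This changes a few sentences. The ratio uses the cost and recruitment data already needed for the planned figure; the one added commitment is to record staff time in both groups, which the protocol now treats as optional.

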10.6.2 Retention SWAT

An 'intention-to-treat' analysis will be performed including all randomised participants analysed in the SWAT group to which they were allocated.

Demographic characteristics, including age, sex, and ethnic group, will be presented descriptively as mean (standard deviation) or number (%), as appropriate.

Primary analysis: Comparison of the questionnaire response rate between the SWAT groups will use logistic regression. The regression model will include the randomised group factor and the SWAT stratification factor (i.e., host trial intervention arms). The between-groups difference will be presented as number (%) and as both adjusted absolute (i.e., risk difference) and relative (i.e., odds ratio or relative risk) effect estimates, with 95% confidence intervals from the logistic regression model.

Any randomised participant who does not provide outcome data for any reason (including participants who were deceased or withdrawn from the host trial) will be categorised as 'No' for the primary outcome.

Secondary analysis: The between-groups difference in time taken to collection of outcome data will be analysed using techniques suitable for time to response (event) data such as Kaplan-Meier curves, log-rank test or Cox regression (adjusted for SWAT stratification/minimisation factors). Time zero will be set as 'day before expected completion date' (equivalent to adding 1 to the time variable to avoid exclusion from the analysis set). The analysis of questionnaire

completeness will be as for the primary outcome. The incremental cost per participant retained will be calculated for the comparisons under evaluation as the difference in costs between the SWAT groups, divided by the difference between groups in completion rates. Direct costs of the retention strategies, and indirect costs associated with administering the strategies and the comparators will be included.

The following sensitivity analyses will be performed for the primary analysis:

- Excluding participants who did/could not receive allocation as randomised.
- Excluding participants who were retrospectively found to have died or withdrawn from the host trial before the expected completion date.

Subgroup analysis may also be performed for key demographic subgroups (e.g. age, gender, ethnicity) by adding interaction terms to the logistic regression or Cox regression model, where the sample size is deemed sufficiently large.

Meta-analyses will include data from existing SWATs and will estimate differences in retention rates between the intervention and comparator groups. Within the meta-analysis, remote self-completion of questionnaires by trial participants and face-to-face data collection should be evaluated in subgroups and a combined treatment effect should be presented only if it is deemed that the effects are homogeneous between subgroups.

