4.0 Trial Design

4.1 Design

The trial objectives will be addressed using a multicentre, two-arm, non-blinded, pragmatic, parallel group randomised controlled superiority trial.

The study will consist of a three-year recruitment phase, including the 12-month internal pilot phase, followed by the main recruitment period. Following collection of baseline measures, randomisation and treatment, all participants will be followed up for 24 months. Follow-up data will be collected from participants via a remote questionnaire every four months, at 4, 8, 12, 16, 20 and 24-months post randomisation.

The 12-month internal pilot will assess recruitment and retention and patient acceptability of both the intervention and trial processes. The pilot study will be set up in sites with existing surgical, rehabilitation and prosthetic experience of TKA, allowing additional time for other sites to receive training and support to implement or expand TKA services if required.

Semi-structured interviews will be conducted to include study participants, those who withdraw from the study and patients who decline to participate. The findings of these interviews will be used to inform aspects of trial design and delivery during this phase. These interviews will take place 8-10 weeks post-treatment.

To understand the longer-term impact of TKA and AKA on patient's lives and recovery, as part of the qualitative study, we will follow up a subgroup of 20-24 patients for up to 3 years, with interviews at 12, 24 and 36 months post-operatively.

A report will be provided to the funder at the end of the pilot phase and subject to their approval (assuming feasibility has been established) will proceed to the main trial.

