4.5.2 Retention SWAT: A cash vs voucher monetary incentive

Poor participant retention rates can have adverse consequences on the validity of randomised trials. There is a lack of evidence on efficient ways to retain participants in trials.

Monetary incentives consisting of either shopping/gift vouchers or cash are a common strategy used by trial teams to encourage participants to complete follow-up

questionnaires, attend follow-up assessment appointments or both. A previous review of strategies to improve retention in trials found monetary incentives may improve retention rates compared with no incentive; but the certainty of the evidence was low [1]. As a result, evaluation of monetary incentives as a retention method requires further evaluation.

We will evaluate the effect of an unconditional £25 shopping voucher incentive compared with an unconditional £25 cash incentive, provided before the 12 and 24 month follow up questionnaire. Participants will be asked to confirm their voucher preference at Baseline so that this can be provided should the participant be randomised to receive the voucher intervention.

As is usual with embedded trials, the sample size is constrained by the number of patients approached about the study hence a formal power calculation to determine sample size has not been conducted.

All participants recruited into the HAMLET trial, who remain as fully participating (i.e. have not fully withdrawn, withdrawn from postal follow up or have died) and who have yet to reach the 12-month time point will be eligible for the SWAT. There are no additional inclusion or exclusion criteria.

Generation of the allocation sequence will be undertaken independently by a researcher not involved with the follow up of participants. Participants will be allocated 1:1 using block randomisation, stratified by the host trial's treatment arm, using randomly varying block sizes to avoid imbalance between the SWAT intervention arms.

The primary outcome of this embedded trial will be retention rate, i.e. the proportion of participants who return their questionnaire in each group.

Secondary outcomes will be:

- 1) Cost-effectiveness (cost per participant retained)
- 3) Number of contact attempts with participants before completion of follow-up

assessment

4) Questionnaire completeness (e.g., primary outcome measure obtained)

The effects of the strategies in different patient populations will be explored, including sex, age and ethnic subgroups.

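### The retention SWAT's primary model is valid but leaves out month-4 and month-8 questionnaire return, a cheap pre-incentive covariate that may add precision

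*Protocol*

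**What the plan says.** Section 10.6.2 of the protocol sets the primary analysis of the retention SWAT as a logistic regression: "The regression model will include the randomised group factor and the SWAT stratification factor (i.e., host trial intervention arms". Adjusted absolute and relative effects are to be reported. None of the primary, secondary or sensitivity analyses listed there uses a participant's earlier response record.

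Section 4.5.2 defines the outcome as "the proportion of participants who return their questionnaire in each group". The incentive is "provided before the 12 and 24 month follow up questionnaire". On size, it says that "a formal power calculation to determine sample size has not been conducted", because the host trial sets the number. On entry, it says "Participants will be allocated 1:1 using block randomisation", stratified by host arm, and that people still fully participating "who have yet to reach the 12-month time point will be eligible for the SWAT". No single moment for SWAT allocation is fixed.

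Section 4.1 gives the schedule: "Follow-up data will be collected from participants via a remote questionnaire every four months", that is, months 4, 8, 12, 16, 20 and 24. Section 10.2 already tracks the month-4 EQ-5D-5L return rate as a pilot progression criterion.

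**The concern.** Two questionnaires, at months 4 and 8, fall due before any incentive is sent. Whether each came back will be on file for participants who reach the first incentive. Past response may well carry information about future response, whereas host-trial arm, the only covariate in the model, has no obvious reason to carry much.

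Section 10.6.2 also counts death or withdrawal after SWAT entry as non-return, so the outcome has several sources of variation that host arm is unlikely to explain.

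With the sample fixed, the confidence interval can be narrowed only through the analysis. If earlier return is prognostic and is left out, the interval for the cash-versus-voucher difference is wider than these data allow. A real difference is then somewhat more likely to be missed.

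**Working it through.** **Ceiling for the SWAT sample.** Section 10.1 gives a difference of 0.074, SD 0.2, 90% power, two-sided 5% and 20% loss.
- n per arm = 2 × (1.960 + 1.282)² × 0.2² / 0.074² = 153.5, so 154.
- 154 / 0.8 = 192.5, so 193 per arm and 386 in total. This reproduces the plan's total, which is the most the SWAT can have. The figure of 183 per arm in the same sentence does not match it; that is a separate matter with no bearing here.

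**Precision of the model as written.** With overall return p and N participants split 1:1, SE of the risk difference = √[4p(1−p)/N].
- N = 386, p = 0.80 (the complement of the 20% loss): √(4 × 0.16 / 386) = 0.041.
- 95% CI half-width: 1.96 × 0.0407 = 8.0 percentage points.
- Difference detectable with 80% power: 2.80 × 0.0407 = about 11 points.

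**Effect of adding prior return.** Let q be the share who returned earlier, a their later return rate, and b the later rate among earlier non-returners. Then p = qa + (1−q)b and R² = q(1−q)(a−b)² / [p(1−p)]. The adjusted SE is about SE × √(1−R²), and the equivalent gain in sample is 1/(1−R²) − 1.

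The protocol gives none of q, a or b, so all are assumptions. N = 330 is also assumed (386 less some deaths and withdrawals).

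| q | a / b | p | R² | SE, as written → adjusted | Gain in sample |
|---|---|---|---|---|---|
| 0.80 | 95% / 30% | 0.820 | 0.16 × 0.4225 / 0.1476 = 0.458 | 0.042 → 0.031 | +85% |
| 0.85 | 93% / 40% | 0.851 | 0.1275 × 0.2809 / 0.1271 = 0.282 | 0.039 → 0.033 | +39% |
| 0.85 | 90% / 50% | 0.840 | 0.1275 × 0.16 / 0.1344 = 0.152 | 0.040 → 0.037 | +18% |
| 0.85 | 88% / 65% | 0.846 | 0.1275 × 0.0529 / 0.1306 = 0.052 | 0.040 → 0.039 | +5% |

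With p held at 0.80, the weakest case examined (q = 0.95, b = 0.60) gives +1%. The strongest corner (q = 0.80, b = 0.20) gives +129%, an extreme I would not plan on.

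**Simulation check** (logistic fits, standardised risk difference, one prior-return term).
- N = 330, 93%/40%: SD falls from 0.040 to 0.034. At 88%/65% it falls from 0.041 to 0.040.
- N = 386, q = 0.85, b = 0.30: SD falls from 0.041 to 0.035-0.036, a gain of about 30-34% where the formula gives 38%. At q = 0.90, b = 0.60 the gain is 0-3%.
- The formula therefore runs slightly high, and I read the favourable range as about 35-80%.
- Power at N = 330: for 85% versus 91% under the 93%/40% assumption, 39% rises to 51%; for 82% versus 88% under the 95%/30% assumption, 31% rises to 48%.
- Type I error with one prior-return term was between about 4% and 6.5% across the simulations, close to the model as written.

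**How many covariates.** At N = 330 and 15-18% non-return there are 330 × 0.15 = 50 to 330 × 0.18 = 59 non-returns. A model with SWAT arm, host arm, month-4 return, month-8 return, age, sex and three-level frailty has 8 parameters, or 6 to 7 non-returns each. In simulation this longer list gave nothing beyond the single prior-return term, and type I error was slightly higher (0.056-0.071 against 0.055-0.065).

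**Timing.** The visit window is ±21 days. From the close of the month-8 window to the opening of the month-12 window is about 122 − 42 = 80 days, so allocation after month 8 is feasible.

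**The case against.** The strongest reply is that nothing here is an error. The model contains the randomised factor and the only stratification factor, it is prespecified, and it holds its type I error. That stands, and a reader who inferred bias or an invalid test would be wrong.

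A reader might also infer that earlier return is known to be a strong predictor. The protocol contains no such figure. Eligibility excludes people who have already died, fully withdrawn or left postal follow-up, which removes many predictable non-returners and may weaken the association. That stands too, and it is why the gain can only be given as a range.

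Nor is it right that the simple model gives up precision for nothing. Section 10.6.2 plans meta-analysis with other SWATs, and a stratification-only model is easier to share across host trials. Adding a prognostic covariate makes the odds ratio more conditional and so less comparable. A standardised risk difference stays marginal, and raw counts can be supplied for pooling, so the cost is manageable but real.

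Finally, someone allocated before month 4 or 8 would have a return status that post-dates allocation. Voucher preference is asked at baseline, so participants may know that an incentive is coming. This is harmless only if the allocation itself is unknown until after month 8. The protocol does not say so, and the fix has to.

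**Conclusion.** The point holds as a small efficiency improvement. The analysis as written would give a sound answer with an interval that may be wider than necessary. How much wider depends on an association that the protocol does not report: the benefit is negligible if earlier non-returners mostly return later, and worth roughly a third or more extra participants if most of them do not. No material loss appeared in the weak cases. Even in the favourable cases shown, power for a six-point difference only reaches about 50%, so the SWAT would still depend on pooling. The conclusion rests on the assumed return rates, on about 330-386 participants, and on prior return being unaffected by SWAT allocation. The host trial's primary result is not touched.

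**What to change.** In section 10.6.2, before any SWAT results are seen:
- Add one prespecified prior-return covariate to the primary logistic model, alongside SWAT group and host arm: either month-8 return (yes/no) or the count of month-4 and month-8 questionnaires returned (0, 1, 2). Do not add age, sex and frailty.
- State in section 4.5.2 that SWAT allocation is made after the month-8 questionnaire or, if made earlier, is not disclosed until after it.
- Use the same pre-incentive covariate for the 12-month and 24-month comparisons. Never adjust a 24-month comparison for return at month 12, 16 or 20, since the incentive can affect these.
- Name the standardised (marginal) risk difference as the main effect.
- Keep the stratification-only model, or raw counts by arm, for the meta-analysis.

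The cost is a few sentences of wording and a rule on allocation timing. No new data, participants or site work are needed. The one downside is an adjusted odds ratio that is less comparable with other SWATs, which the retained simple model or raw counts cover.
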